1. ABBREVIATIONS, ACRONYMS AND DEFINITIONS

All Suture-Based Technique: A repair technique (all-inside, inside-out, outside-in or combination thereof) utilizing only suture without implanting any other material intended to anchor and/or replace suture material.

BMI: Body Mass Index

Complex Tear: Multiple discreet tears, tears with multiple planes, or meniscal tissue incapable of holding suture.

Consented Patient: A patient who, after the screening process, grants consent to participate in the trial.

CFR: Code of Federal Regulations

CRF: Case Report Form; includes all study forms.

Enrolled Subject: A patient who has been consented, meets all criteria for inclusion immediately prior to treatment and receives all suture-based repair of meniscal tear.

HT: Horizontal tear (of the meniscus); the majority of the tear is oriented primarily (but not exclusively) parallel to the plane of knee joint dividing the structure into superior and inferior flaps. For the purpose of this protocol, HT includes obliquely-oriented tears. These tears may open at the central apex or along the inferior surface of the meniscus. Some horizontal tears may have a radial component (bird beak) in the central White Zone.

HIPAA: Health Insurance Portability and Accountability Act

IKDC: International Knee Documentation Committee

IRB: Institutional Review Board

ISAKOS: International Society of Arthroscopy, Knee Surgery and Orthopaedic Sports Medicine

KOOS: Knee injury and Osteoarthritis Outcome Score

PCL: Posterior Cruciate Ligament

Protocol Deviation: A protocol deviation is any change, divergence, or departure from the study design or procedures of a research protocol that is under the Investigator's control and that has not been approved by the IRB.

Protocol Violation: A protocol violation is a deviation from the IRB-approved protocol that may affect the subject's rights, safety, or well-being and/or the completeness, accuracy and reliability of the study data.

Red Zone: The well-vascularized peripheral-most ~30% of the meniscus.

Red-White Zone: The transition between the outermost and innermost portions of the meniscus where vascularity diminishes from peripheral to central.

Subject: A consented patient who has been enrolled in the study.

White Zone: The inner (avascular) one-third of the meniscus.

2. PROTOCOL SYNOPSIS

Study Title	A Prospective, Non-randomized, Multi-center Investigation of All Suture-based Repair of Horizontal Meniscal Tears
Protocol Number	CTX-CP001
Study Objectives	The primary objectives of this study are to document horizontal meniscus tear repair, characterize the reoperation survival curve and assess improvements in knee pain and function.
Study Design	Interventional, non-randomized, single-arm assignment, open label clinical trial of suture-based meniscal repair.
Endpoints	Freedom from reoperation of the index meniscus repair site at 6 months, 1 year, and 2 years; Improvements in knee pain and function as measured by KOOS, IKDC Knee evaluation, Lysholm Knee scale and Tegner Activity Scale
Subject Population	The study population will include 30 otherwise healthy subjects 18 to 60 years of age (inclusive), enrolled at up to 10 investigational sites in the United States, who have a horizontal meniscus tear.
Analysis Populations	Data obtained from all enrolled subjects will be analyzed on a per-treatment (PT) basis, which will include all enrolled subjects who receive the protocol-defined treatment of suture-based meniscal repair.
Study Duration	Subjects will be followed for a total of 2 years.
Screening Inclusion Criteria	Subjects of either gender may be eligible for inclusion in the study only if they meet all of the following criteria at screening: 
• Able and willing to give informed consent by voluntarily providing written informed consent in accordance with governing Institutional Review Board• 18 to 60 years of age, inclusive at the time of screening;• History indicative of meniscal pathology (e.g., pain, mechanical symptoms described as locking, clicking or giving way);• Physical exam consistent with meniscus tear (e.g., locked joint, joint line tenderness and/or pain on meniscal compression);

	
 • If prior ligament reconstruction, the study knee is clinically stable; • Preoperative MRI evidence consistent with a horizontal/oblique meniscus tear in the symptomatic compartment; • Healthy and not pregnant

Screening Exclusion Criteria
	
Subjects will be excluded from the study for any of the following reasons during screening:
 
 • Arthritis in the study knee (Kellgren-Lawrence Grade 3 or higher); • Body Mass Index (BMI) ≥ 35 kg/m²; • Previous meniscal repair or meniscectomy of the study meniscus; • Unstable knee; • Malalignment of the study knee >5 degrees and/or requiring osteotomy and/or correction; • History of constitutional/systemic inflammatory/arthritis problem or pain condition, history of knee infection, vascular condition of legs, benign neoplasms of knee, hepatitis, HIV, drug/alcohol abuse, tobacco abuse, cancer; • Expected to undergo any other primary treatment of the knee; • Any concomitant painful or disabling disease, condition or post-procedure status of either lower extremity that would interfere with evaluation or rehabilitation of the study knee. • Pregnant or planning to become pregnant in the next 2 years.

Arthroscopy Inclusion Criteria
	
Consented subjects may be included in the study only if, upon arthroscopic inspection, their meniscal study lesion meets all of the following criteria established by the International Society of Arthroscopy, Knee Surgery and Orthopaedic Sports Medicine (ISAKOS):
 
 • Zone location: circumferential location of tear includes locations within 10mm of the peripheral rim of the meniscus; • Radial location: any location from anterior to posterior; • Tear pattern: primarily horizontal or oblique in orientation (not to exceed 45 degrees from horizontal);

	
 • Compartment: either lateral or medial, but not both; • Opposite compartment meniscal tear (if present) limited to the central portion (i.e., Zone 3/“white zone”); • Tear amenable to repair with all suture-based techniques.

Arthroscopy Exclusion Criteria
	
Subjects will be excluded from the study if their study meniscus lesion meets any of the following criteria at arthroscopy:
 
 • Tear pattern: primarily vertical longitudinal or radial in orientation; • Partial meniscectomy of any portion of the study meniscus extends beyond the central portion (i.e., Zone 3/“white zone”); • Intact or partially intact meniscus tear that, in the opinion of the Investigator, does not require repair; • Poor meniscal tissue quality such that it will not hold a suture; • Any portion of the meniscus repair that, in the opinion of the Investigator, is best treated using an implant other than suture; • Clinically significant (zone 1 and/or zone 2) tear in the contralateral compartment to the study meniscus; • Performance of a significant concomitant procedure intended as a therapeutic intervention on the study knee; • Arthritis in the surgical knee Modified Outerbridge Grade III or higher.

Study Visits
	
Screening (Study Visit 1): Informed consent, screening eligibility criteria, demographics, patient reported outcomes, MRI (within 6 months) and X-rays (within 6 months);
 
Procedure (Study Visit 2): Arthroscopy eligibility criteria, enrollment, meniscal-repair, images, complications; details of pathology and procedure
 
1st postop [Day 7-15] (Study Visit 3): Complications;
 
2nd postop [Day 90±7 days] (Study Visit 4): Complications, patient reported outcomes;
 
3rd postop [Day 185±14 days] (Study Visit 5): Complications, patient reported outcomes, visual examination of meniscus tear (when available);

	4th postop [Day 365±30 days] (Study Visit 6): Complications, patient reported outcomes, MRI; 5th postop [Day 730±30 days] (Study Visit 7): Complications, patient reported outcomes, X-Rays;
Rehabilitation Plan	All subjects will follow their Investigator’s preferred rehabilitation plan. At a minimum, all subjects must meet the following post-operative thresholds: 
 • Weight bearing as tolerated • Hinged knee brace locked in extension when walking (4-6 weeks), released to 90 degrees for sitting/driving • No squatting or stand up/sit down motions until after 6 weeks post-op • No cutting or pivot sports until after 6 months post-op
Sponsor	Ceterix Orthopaedics [name] [name] [contact]

3. INTRODUCTION, BACKGROUND AND RATIONALE

This document is a protocol for a human research study. This study is to be conducted in accordance with United States government research regulations, applicable international standards of Good Clinical Practice and institutional research policies and procedures.

3.1. Background

Meniscal pathology, primarily in the form of a tear, is very common and frequently symptomatic. In the United States alone, over 500,000 meniscectomies were performed in 2006.¹ Historically, treatment for meniscal tears consisted of open total meniscectomy. As surgeons began evaluating the long-term impact of total meniscectomy and, in parallel, as biomechanical studies began demonstrating the vital importance of the meniscus on knee function,^{2,3,4,5,6,7,8,9} it became apparent meniscectomy had consequential and deleterious effects on the knee over time.^{10,11,12,13} An interest in improving the treatment of meniscal pathology emerged in the orthopedic community.

As the understanding of the importance of the meniscus evolved, so too did technologies enabling surgeons to perform more specific and limited procedures on torn menisci with arthroscopic approaches.¹⁴ As a result, many patients have undergone arthroscopic-assisted meniscus-preserving surgery (limited removal, repair or a combination of the two procedures) over the past 30 years. Compared to outcomes when total meniscectomy was standard of care, clinical outcomes for patients with meniscal tears today have improved substantially.¹⁵ Although less

anatomical destruction is the preferred strategy, when a tear is deemed not amenable to repair, partial meniscectomy is the next line of treatment.

Although repair when feasible is the current standard of care for meniscal tears,^{16,17,18,19,20,21,22,23,24} it is most often performed on primarily, vertically-oriented tears for several reasons. Firstly, the anatomic constraints of the knee limit arthroscopic placement of sutures and non-suture devices in such a way that a perpendicular approach to the tear is the least technically challenging. Vertical tears present in a substantially perpendicular plane relative to the arthroscopic access ports. Secondly, the literature is replete with data demonstrating a high efficacy rates in these tears.^{25,26,27,28,29,30,31}

Reparability and healing potential are not identical; however the concepts are often used interchangeably. One term is correctly applied to the technical feasibility of performing a repair and maintaining the repair integrity over time; the other is a biologic phenomenon. The current teaching regarding horizontal/oblique and tears is that they are most often irreparable.^{32,33,34,35,36} As such, little clinical documentation regarding the feasibility of repairing these tears exists. Furthermore, contrary to clinical doctrine, the scant existing literature on the subject challenges the understanding of the healing potential of horizontal/oblique tears by suggesting that repair has successful outcomes anywhere from 50-100% of the time.^{37,38,39,40,41,42,43,44} Clearly additional prospective assessments of horizontal/oblique tears is needed.

Horizontal tears are notable for a few reasons: 1) they are common, comprising up to 20% of meniscus tears^{45,46,47}; 2) despite improvements in meniscal repair methods, the techniques have been difficult to employ successfully across these particular tears. With newer suture delivery methods enabling surgeons to more easily place sutures in patterns that reduce these tears, it is possible to further assess and document their reparability. This study will begin that process by examining and documenting the ability to successfully repair horizontal meniscus tears using all suture based techniques.

3.2. Rationale and Justification for the Study

a. Rationale for the Study Objectives

Although the clinical consensus holds that horizontal tears are often irreparable, there are no prospective, multi-center trials in the literature that document successful repair of the meniscus, surgical reoperation rates for meniscal tears and improvements in knee pain and function.

b. Rationale for Study Population

The study is limited to healthy subjects with horizontal meniscal tears. Although these injuries can occur in any age group, slightly younger age range (18-60 years of age) allows inclusion of knees with less likelihood of significant arthritic changes

which may mask measurement of knee pain and function improvements following the treatment procedure.

c. Rationale for Study Design

It is well established in the literature that meniscectomy leads to increased risk of late osteoarthritis, and conversely, that repairing the meniscus reduces this risk. The clinical consensus is that preservation of meniscal tissue should be the goal whenever possible. The alternative for these patients is meniscectomy (a failure endpoint in this study), therefore there is no available control. A prospective, non-randomized, single-arm assignment study design is the best method for obtaining objective data for clinicians and patients in weighing the viability of meniscal repair versus primary meniscectomy.

4. STUDY DESIGN

4.1. Hypotheses

No formal hypotheses testing will be done. However, primary outcome measures that will be examined include: A substantial proportion of the subjects will show meniscus healing at 6 months. The two-year reoperation survival rate will be similar or less than historical rates. Patient reported outcomes will be improved at six-months following the procedure.

4.2 General Design

The study is an interventional trial designed as a non-randomized, single-arm, open-label study of repairs of horizontal of the meniscus using commercially available products. The study will enroll 30 subjects at up to 10 investigational sites in the United States.

4.3. Objectives

The primary objectives of this study are to assess reoperation rate, improvements in knee pain and function, and meniscus repair rate following all-suture-based repair of the horizontal meniscal tear.

4.4. Potential Risks and Benefits

a. Risks of Study Participation

A subject has the risk of suture reaction, a risk that exists with any surgical procedure utilizing suture material. Additionally, although some studies suggest that repairing horizontal tears can be effective, this may not be the case in this study. Some or all subjects in the study may fail to gain relief of their symptoms or have a recurrence of their symptoms, necessitating subsequent surgical procedures to solve their pain and mechanical symptoms.

In-office needle arthroscopy (e.g. VisionScope) diagnostic testing risk is minimal. The probability and magnitude of harm or discomfort anticipated in this research study is no greater than that ordinarily encountered during the performance of routine diagnostic tests. The diagnostic device used in this study is approved for diagnostic procedures by the FDA and therefore this study does not present new risks to patients and should be considered a non-significant risk study based upon the definitions in 21 CFR 812.3. The most common risk associated with an in-office needle arthroscopy procedure is slight pressure or discomfort from needle/device insertion. Least common risks are minor bleeding in and around the joint area. And while rare, there is always a risk of infection in the joint due to the introduction of a foreign object in the body. Device-related potential complications are minimal. The currently available device (VisionScope) has already passed rigorous electrical safety, electromagnetic compatibility, biocompatibility and sterility testing from its FDA 510(k) submission process, as documented per the VisionScope Quality System Manual and filed in the FDA 510(k) summary:

http://www.accessdata.fda.gov/cdrh_docs/pdf10/K101734.pdf.

At a bare minimum, currently employed standards of care for in-office arthrocentesis techniques will be used for in office arthroscopy procedures. This includes sterile preparation with betadine and alcohol, and sterile draping.

Patient follow-up will be governed by the treating physician's traditional post-operative regime for knee arthroscopies and repairs.

b. Potential Benefits of Participation

A large body of evidence exists to support the concept that successful meniscus repair facilitates long-term joint preservation. In spite of this, it is uncommon for horizontal meniscus tears to be repaired. Participation in this study provides a subject the opportunity to receive a repair of the torn meniscus, which is not widely performed within the medical community. The patient will also gain the benefits of an anatomy preserving procedure and to contribute to a growing body of evidence regarding joint preservation. If the procedure is effective, subjects may obviate or substantially delay the need for additional reconstructive procedures on their knees in the future.

4.5. Study Assessments

For timing of study assessments activities and visit windows see Section 14.

a. Outcome Assessments

- International Knee Documentation Committee Subjective Knee Evaluation Form (IKDC Knee Evaluation)
- Knee Injury and Osteoarthritis Outcome Score (KOOS)
- Lysholm Knee Questionnaire
- Tenger Activity Scale
- In-office needle arthroscopy assessment of meniscus repair (when performed)

- Freedom from reoperation on the index meniscus repair site;
- Condition of meniscal tissue per MRI (Appendix 7);
- Joint condition per X-ray (Appendix 7).

b. Safety Variable (see Section 7.1 for definitions)

- Safety follow-up

c. Patient and Procedural Variables

- Patient demographics and knee pathology history
- Details of procedure
- Details of tear

5. STUDY POPULATION

5.1. Planned Number of Subjects

A total of 30 subjects will be enrolled.

5.2. Criteria for Recruitment

a. Diagnosis and Main Criteria for Enrollment

Subjects will be recruited for the study through the clinical practices of the Investigators. The study population includes otherwise healthy subjects with a symptomatic meniscus tear, who are able and willing to participate and who qualify for study inclusion based on specific eligibility criteria.

The presence of some inclusion or exclusion criteria cannot be detected by preoperative clinical or radiologic evaluations and it is only after the surgeon has inserted the arthroscope to inspect the knee joint visually that the presence of such injuries or disorders can be detected. Consented subjects will only be enrolled at the time of arthroscopy provided a qualifying meniscal tear is confirmed, no other exclusionary findings are encountered and the meniscal tear is surgically treated.

b. Inclusion Criteria

Screening Inclusion Criteria:

Subjects of either gender *may be* eligible for inclusion in the study only if they meet *all* of the following criteria:

- Able and willing to give informed consent by voluntarily providing written informed consent in accordance with governing Institutional Review Board
- 18 to 60 years of age, inclusive at the time of screening;
- History indicative of meniscal pathology (e.g., pain, mechanical symptoms described as locking, clicking or giving way);
- Physical exam consistent with meniscus tear (e.g., locked joint, joint line tenderness and/or pain on meniscal compression);

- If prior ligament reconstruction, the study knee is clinically stable;
- Preoperative MRI evidence within 6 months consistent with a horizontal/oblique meniscus tear in the symptomatic compartment
- Healthy and not pregnant

Arthroscopy Inclusion Criteria:

Consented subjects **may be** included in the study only if, upon arthroscopic inspection, their meniscal study lesion meets **all** of the following criteria established by the International Society of Arthroscopy, Knee Surgery and Orthopaedic Sports Medicine (ISAKOS) (see Appendix 1):

- Zone location: circumferential location of tear includes locations within 10mm of the peripheral rim of the meniscus;
- Radial location: any location from anterior to posterior;
- Tear pattern: primarily horizontal or oblique in orientation (not to exceed 45 degrees from horizontal);
- Compartment: either lateral or medial, but not both;
- Opposite compartment meniscal tear (if present) limited to the central portion (i.e., Zone 3/“white zone”);
- Tear amenable to repair with all suture-based techniques.

c. Exclusion Criteria

Screening Exclusion Criteria:

Subjects **will be** excluded from the study for **any** of the following reasons:

- Arthritis in the study knee (Kellgren-Lawrence Grade 3 or higher [See Appendix 4]);
- Body Mass Index (BMI) ≥ 35 kg/m²;
- Previous meniscal repair or meniscectomy of the study meniscus;
- Unstable knee;
- Malalignment (> 5 degrees) of the study knee, based on X-ray within 6 months requiring osteotomy and/or requiring correction;
- History of constitutional/systemic inflammatory/arthritis problem or pain condition, history of knee infection, vascular condition of legs, benign neoplasms of knee, hepatitis, HIV, drug/alcohol abuse, tobacco abuse, cancer;
- Expected to undergo any other primary treatment of the knee;
- Any concomitant painful or disabling disease, condition or post-procedure status of either lower extremity that would interfere with evaluation or rehabilitation of the study knee.
- Pregnant or planning to become pregnant in the next 2 years.

Arthroscopy Exclusion Criteria:

Subjects **will be** excluded from the study if their study meniscus lesion meets **any** of the following criteria at arthroscopy:

- Tear pattern: primarily vertical longitudinal or radial in orientation;
- Partial meniscectomy of any portion of the study meniscus extends beyond the central portion (i.e., Zone 3/“white zone”);
- Intact or partially intact meniscus tear that, in the opinion of the Investigator, does not require repair;
- Poor meniscal tissue quality such that it will not hold a suture;
- Any portion of the meniscus repair that, in the opinion of the Investigator, is best treated using an implant other than suture;
- Clinically significant (zone 1 and/or zone 2) tear in the contralateral compartment to the study meniscus;
- Performance of a significant concomitant procedure intended as a therapeutic intervention on the study knee;
- Arthritis in the surgical knee Modified Outerbridge Grade III or higher [See Appendix 2 and 3]).

5.3. Withdrawal Criteria

Subjects may withdraw from the study at any time prior to the subject’s expected completion and for any reason without prejudice to further treatment. Subjects considered treatment failures will be withdrawn from the study to receive appropriate alternative treatment.

A subject’s participation in the study may be discontinued at any time prior to the subject’s expected completion at the discretion of the Investigator or Sponsor. Reasons for removing a subject from the study include, but are not limited to, the following:

- The subject is uncooperative in adhering to the protocol requirements, including failure to participate in rehabilitation;
- The Investigator believes it is in the best interests of the subject;
- The subject withdraws consent.

The Investigator will attempt to document the subject’s reason for withdrawal on the study completion CRF.

If a subject fails to attend study visits, every attempt shall be made to contact the subject prior to considering the subject lost to follow up and withdrawing the subject from the study.

Subjects who are withdrawn from the study will not be replaced.

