Investigator-specific standard-of-care arthroscopy will be performed. Intraoperative eligibility criteria will be evaluated. If **all** of the arthroscopy inclusion criteria are met and **none** of the arthroscopy exclusion criteria are met, the subject will be eligible for study enrollment. The subject is officially enrolled in the trial when the meniscal repair is completed.

Meniscal Repair Procedure

The Investigator will follow standard all-inside and/or inside-out, and/or outside-in, and/or NovoStitch arthroscopic procedures:

- Recommended spacing of sutures is 5mm;
- Video, still photographs and diagrams of the arthroscopy procedure will be captured for documentation of meniscal tear, tear preparation and tear treatment parameters. Images and diagrams will be provided to the sponsor. All patient identifying information should be removed prior to transferring images to the sponsor.

The ISAKOS Questionnaire documenting details of the meniscus tear and required excision (if any) will be completed (CRF-004, Details of Pathology). Details of the procedure will be documented (CRF-005, Details of Procedure) will be completed. It contains questions regarding the following:

- Number and configuration of sutures used;
- Repair technique and instruments;
- Meniscal repair time recorded from intraarticular introduction of suture to transection of final suture knot;
- Other intraoperative findings.

Rehabilitation Procedure

All subjects will follow their Investigator's preferred rehabilitation plan based on the particular tear and repair characteristics. At a minimum, all subjects must meet the following post-operative thresholds:

- Weight bearing as tolerated
- Hinged knee brace locked in extension when walking (4-6 weeks), released to 90 degrees for sitting/driving
- No squatting or stand up/sit down motions until after 6 weeks post-op
- No cutting or pivot sports until after 6 months post-op

c. First Follow-up [7-15 days] (Study Visit 3)

Subjects will be evaluated and a safety follow-up will be completed.

d. Second Follow-up [90 Day \pm 7 days] (Study Visit 4)

All subjects will be evaluated and a safety follow-up form will be completed. In addition all subjects will complete the following:

- KOOS
- IKCD Knee Evaluation
- Lysholm Knee Questionnaire
- Tegner Activity Scale

e. Third Follow-up [185 Day \pm 14 days] (Study Visit 4)

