9. STATISTICAL PLAN

9.1. Subject Population(s) for Analysis

Data obtained from all enrolled subjects will be analyzed on a per-treatment (PT) basis, which will include all enrolled subjects who receive the protocol-defined treatment of suture-based meniscal repair.

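### Protocol 5.3 permits removal of a repaired subject for non-adherence with no further outcome collection, and SAP 7.2 to 7.4 then drop that subject from the primary results, which can bias them in favour of the repair

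*Protocol*

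**What the plan says.** Enrolment is complete only after treatment: "The subject is officially enrolled in the trial when the meniscal repair is completed" (Protocol 6.2). Any removal for poor rehabilitation therefore happens after the repair.

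Protocol 5.3 allows participation to be ended early "at the discretion of the Investigator or Sponsor". The listed reasons, which are expressly not exhaustive, include "The subject is uncooperative in adhering to the protocol requirements, including failure to participate in rehabilitation". The same section says "Subjects who are withdrawn from the study will not be replaced" and, separately, "Subjects considered treatment failures will be withdrawn from the study to receive appropriate alternative treatment". It does not say that outcome data will be collected after removal. The only collection after exit that the protocol mentions is vital status where privacy authorization has been revoked (8.2).

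On rehabilitation, Protocol 6.2 leaves the plan to each investigator but adds a floor: "At a minimum, all subjects must meet the following post-operative thresholds".

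Protocol 9.1 defines the analysis population as "all enrolled subjects who receive the protocol-defined treatment of suture-based meniscal repair", with no condition on adherence or completion. The SAP is narrower:
- **7.2:** the Analysis Population excludes subjects with significant deviations and those who left early. The all-treated Safety Population is assigned to disposition, deviations and safety only.
- **7.3:** data are analysed as observed cases.
- **7.4:** the denominator for freedom from reoperation counts only subjects whose repair status is known.
- **6.1:** 30 subjects were accrued, and 3 are left out of all analyses because of protocol deviations whose type is not given.

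**The concern.** The study is open-label and single-arm. Whoever decides on removal can know how the knee is doing, and no control group would show that removals were selective. The protocol imposes minimum rehabilitation conditions on everyone, so it is reasonable to suppose that subjects who ignore them may fail more often. If some are removed and not followed, the remaining subjects are a selected group, chosen after treatment on something that may be related to outcome.

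Freedom from reoperation and the knee scores are the SAP's primary endpoints (5.1), and Protocol 4.1 means to set the two-year reoperation result beside historical rates. Readers will take the figures as the experience of everyone who had the repair. With 30 subjects, a few selective losses move the estimate noticeably.

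**Working it through.** **No design figure to reproduce.** SAP 6.1 says there was no sample size calculation. Neither document gives an expected reoperation rate, a dropout rate or a number removed for non-adherence. The only available arithmetic is 30 − 3 = 27 subjects left after the exclusions in SAP 6.1.

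**How a removal reaches the result.** The SAP does not clearly name the population for the primary endpoints. The Analysis Population is described as supportive, and no other population is assigned to reoperation or function. There are two cases:
1. If the Analysis Population is used, a removed subject counts as having left early and is excluded altogether, including data collected before removal.
2. If all treated subjects are used, as in Protocol 9.1, a removed subject has no data at later visits. Observed-case analysis and the known-status denominator then drop that subject from each later time point.

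Either way the 2-year result omits the subject. Protocol 9.1 cannot prevent this, because a population definition does not supply outcomes that were never collected.

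**Size, on assumed inputs.** Let N = 30 treated, k removed before any reoperation and not followed, p the reoperation risk in those kept and q the risk in those removed.

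- All-treated rate = [(N − k)p + kq] / N
- Rate reported = p
- Understatement = k(q − p) / N

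Only N comes from the documents; k, p and q are assumptions. With p = 10%:

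| k removed | q | All-treated rate | Reported | Understatement |
|---|---|---|---|---|
| 0, or any k with q = 10% | – | 10.0% | 10.0% | 0 points |
| 1 | 30% | (29×0.10 + 1×0.30)/30 = 10.7% | 10.0% | 0.7 |
| 3 | 30% | (27×0.10 + 3×0.30)/30 = 12.0% | 10.0% | 2.0 |
| 5 | 40% | (25×0.10 + 5×0.40)/30 = 15.0% | 10.0% | 5.0 |
| 3 | 100% | (27×0.10 + 3×1.00)/30 = 19.0% | 10.0% | 9.0 |
| 6 | 100% | (24×0.10 + 6×1.00)/30 = 28.0% | 10.0% | 18.0 |

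The last two rows are extremes.

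**Whole-number example with the SAP's Clopper-Pearson interval.** Suppose 6 of 30 treated subjects would be reoperated. With full follow-up, 24/30 = 80.0% are free of reoperation (95% CI 61.4 to 92.3). If 3 of the 6 are removed before their reoperation, the result is 24/27 = 88.9% (70.8 to 97.6).

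The scores are affected in the same direction if removed subjects improve less. The documents give nothing from which to quantify that.

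**The case against.** The strongest reply is that 5.3 alone excludes nobody from analysis. It is permissive, Protocol 9.1 keeps all treated subjects, and data before removal remain usable. That is correct as far as it goes; the loss arises only when 5.3 is combined with the absence of later follow-up and with SAP 7.2 to 7.4. The combination is what the plan prescribes, so the point survives.

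Other parts of the reply stand and limit what can be said:
- A reader might infer that the results will describe adherent subjects only. The documents do not support that. Removal is optional, non-adherent subjects can remain, and no adherence measure defines who would go.
- A reader might take missed rehabilitation as an established cause of repair failure. Neither document says so; the minimum thresholds only suggest relevance.
- A reader might link the 3 exclusions in SAP 6.1 to rehabilitation. Their deviation type is not stated.
- Removals would not be hidden. Protocol 5.3 asks the investigator to try to record the reason on the study completion form, and SAP 7.6 summarises and lists the reasons. No form title in Appendix 6 concerns rehabilitation adherence, but the forms are not in the text reviewed, so it cannot be said that adherence goes unrecorded.
- Sampling error is large beside a shift of 2 to 5 points: for 3/30 reoperated, the exact interval runs from 2.1% to 26.5%. No formal hypothesis is tested. But a wide interval does not cover a bias that always points the same way.

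**Conclusion.** The concern holds in a limited form. The plan allows discretionary removal after treatment for non-adherence, provides no later outcome collection, and has SAP rules that drop such subjects from the primary results even though Protocol 9.1 retains them. If removed subjects are at higher risk, the results favour the repair.

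The size cannot be determined from the documents. It is zero if nobody is removed or if risks are equal. It is 2 points for 3 of 30 removed at 30% risk and 5 points for 5 of 30 at 40%, taking 10% risk in those kept. These figures also assume that each removal precedes any reoperation and that status is never recovered. They are illustrations, not estimates. The point is worth correcting because the endpoints are primary, the sample is small and the remedy is cheap.

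**What to change.** **Protocol 5.3.** State that non-adherence does not end follow-up, and that scheduled assessments and reoperation status are collected to 2 years for every repaired subject unless consent is withdrawn. Reconcile this with the sentence in the same section that withdraws treatment failures. The change concerns data collection only, not what care a subject receives.

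**SAP 7.2 and 7.9.** Name all treated subjects, as in Protocol 9.1, as the population for reoperation and function. State that non-adherence with rehabilitation, wherever it is recorded, is not a ground for exclusion. Recording it on the deviation form (CRF-010) without this statement could backfire, because SAP 7.2 excludes significant deviators. Protocol section 1 also limits deviations to matters under the investigator's control, so it is unclear whether a subject's own non-adherence is one.

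**Reporting.** Give removals by reason. For subjects already removed, recover reoperation status where consent allows. As sensitivity analyses, show results without non-adherent subjects and a worst case in which removed subjects with unknown status count as reoperated.

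**Cost.** A short protocol amendment and a SAP revision. The SAP, dated 4 September 2019, says the sample was already accrued, so the amendment may come too late for many subjects; the SAP change and the recovery of status do not depend on it. Some non-adherent subjects will still miss visits, and the headline rate may be slightly less favourable.
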